**Patients whose tumors remain unresectable at the completion of planned therapy will be considered to have experienced an adverse EFS event. No further protocol therapy is planned for such patients. These patients can be treated at the discretion of the primary physician.**

Patients with pulmonary metastases will receive the first 2 cycles of Regimen H chemotherapy described above. If metastases disappear with chemotherapy, no pulmonary surgical intervention will be performed. If metastases are persistent after 4 total cycles of C5VD chemotherapy and the patient is considered a candidate for liver transplant at that time, metastases are to be resected to render the patient free of extrahepatic disease prior to transplant. Transplant may then be undertaken. If the liver tumor can be primarily resected after either 2 or 4 cycles of C5VD chemotherapy without transplant, this should be performed and the final cycles of chemotherapy should be administered. If the metastases are still present, they should then be resected. Pulmonary metastectomy may be performed earlier in the course of therapy if it can be done without resulting in delays in the administration of scheduled chemotherapy.

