## **8.0 CRITERIA FOR REMOVAL FROM PROTOCOL THERAPY AND OFF STUDY CRITERIA**

### **8.1 Criteria for Removal from Protocol Therapy**

- a) Progressive disease.
- b) Unresectability of tumors following 4 cycles of chemotherapy in intermediate-risk patients.
- c) Unresectability of tumors following 10 cycles of chemotherapy in high-risk patients who responded (RECIST CR or PR) to “up-front” window therapy.
- d) Unresectability of tumors following 8 cycles of chemotherapy in high-risk patients who did not respond to “up-front” window therapy.
- e) Inability to have a liver transplant by the specified protocol timepoints for reasons unrelated to hepatoblastoma.
- f) Failure to begin protocol therapy within 42 days of initial biopsy or definitive surgery whichever occurs last.
- g) Failure to resume post resection chemotherapy within 42 days of resection in intermediate- or high-risk patients.
- h) Refusal of further protocol therapy by patient/parent/guardian.
- i) Completion of planned therapy.
- j) Physician determines it is in patient’s best interest.
- k) Development of a second malignant neoplasm.
- l) For high-risk patients, if the investigator selects a post-induction regimen that is not indicated by the central review of response.

Patients who are off protocol therapy are to be followed until they meet the criteria for Off Study (see below). Follow-up data will be required unless consent was withdrawn.

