### 9.2 Statistical Analysis Methods

#### Statistical Considerations

Patients will be enrolled to the study for Five years and followed for an additional year, by which time we expect most disease-related analytic events will have occurred. The design objectives will be different for the four subgroups: (1) Stage I PFH patients (stratum 1) with AFP  $\geq$  100 ng/mL or AFP not obtained prior to surgical resection of tumor; (2) low risk patients (stratum 2) defined as patients with Stage I non-PFH, non-SCU; Stage II non-SCU (3) intermediate risk patients (stratum 3); and (4) Stage IV patients or patients with AFP < 100 ng/mL at diagnosis (stratum 4). EFS will be the time from patient enrollment until last follow-up or an analytic event is observed, whichever comes first. Analytic events are: (1) progression of existing disease or occurrence of disease at new sites; (2) treatment failure defined as the presence of disease after four cycles of chemotherapy and post-induction surgery (if attempted) for patients enrolled with Stage III disease or presence of disease after planned chemotherapy (eight cycles for non-responders, ten cycles for responders) for patients enrolled with Stage IV disease (3) death from any cause prior to disease progression or diagnosis of a second malignant neoplasm; or (4) diagnosis of a second malignant neoplasm. Survival will be the time from enrollment until death from any cause or last follow-up, whichever comes first.

[Section 3](#) requires that planned start of systemic therapy for patients whose protocol prescribed therapy includes chemotherapy must be within 42 days of enrollment. Experience from prior COG studies of hepatoblastoma demonstrates that this can be accomplished in most patients. All patients who die within 42 days of enrollment will be considered in the analytic plans below. All patients who survive more than 42 days after enrollment and whose protocol therapy prescribes chemotherapy but who do not have such systemic therapy started by the 43rd day after enrollment will be excluded from the analyses below.

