### 13.3 **Surgical Management of Pulmonary Metastasis**

Patients presenting with pulmonary metastatic disease (Stage IV) will receive the “up-front” window chemotherapy described above for high-risk patients. If metastases disappear with chemotherapy, no pulmonary surgical intervention will be performed. If metastases are persistent after 4 total cycles of C5VD chemotherapy and the patient is considered a candidate for liver transplant at that time, metastases are to be resected to render the patient free of extrahepatic disease prior to transplant. Transplant may then be undertaken.

If the liver tumor can be primarily resected after either Cycles 4 or 7 in high risk responders and after Cycles 4 or 6 in high-risk non-responders without transplant, this should be performed and the final cycles of chemotherapy should be administered. If the metastases are still present, they should then be resected. Pulmonary metastectomy may be performed earlier in the course of therapy if it can be done without resulting in delays in the administration of scheduled chemotherapy.

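### The Stage IV treatment-failure event in Section 9.2 is scored at the end of chemotherapy, before the resection of persisting lung metastases that Sections 4.6 and 13.3 plan after the final cycles

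*Combined protocol and SAP*

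**What the plan says.** Section 9.2 lists the analytic events for EFS. For Stage IV, treatment failure is "presence of disease after planned chemotherapy (eight cycles for non-responders, ten cycles for responders) for patients enrolled with Stage IV disease". The companion clause for Stage III reads "presence of disease after four cycles of chemotherapy and post-induction surgery (if attempted) for patients enrolled with Stage III disease", so it names surgery where the Stage IV clause does not.

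Section 4.6 deals with Stage IV patients whose liver tumor can be resected without transplant after 2 or 4 cycles of C5VD: "this should be performed and the final cycles of chemotherapy should be administered". It continues: "If the metastases are still present, they should then be resected". Section 13.3 repeats the sequence: "this should be performed and the final cycles of chemotherapy should be administered. If the metastases are still present, they should then be resected". Both sections then allow an exception; in 4.6 it is "Pulmonary metastectomy may be performed earlier in the course of therapy if it can be done without resulting in delays".

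Section 4.6 also has its own EFS statement: "Patients whose tumors remain unresectable at the completion of planned therapy will be considered to have experienced an adverse EFS event". The off-therapy criteria in Section 8.1 use the same idea, for example "Unresectability of tumors following 10 cycles of chemotherapy in high-risk patients who responded".

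Section 7.5 (footnote 5) and Section 15.3 (footnote 4) call for disease evaluation after Cycle 8 in non-responders and Cycle 10 in responders, unless all tumor has already gone.

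**The concern.** On the pathway that 4.6 and 13.3 describe, disease can be documented by a required scan at the moment 9.2 scores failure, while the operation meant to remove it is still to come. EFS then records the order of surgery and chemotherapy as well as disease control.

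At stake is Stage IV EFS where it feeds aim 1.3.3 (which includes referred patients resected without transplant) and aim 1.3.8 (EFS by prognostic factor). Any EFS comparison by timing of metastasectomy would be biased by definition. In addition, 9.2 and 4.6 test different things, presence of disease and unresectability. Two analysts could therefore score the same patient differently.

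**Working it through.** **1. Trace two patients through the text.** Both are Stage IV window non-responders (8 planned cycles), have the liver tumor resected without transplant after Cycle 6, and have one resectable lung nodule.

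| | Patient A | Patient B |
|---|---|---|
| Metastasectomy | After Cycle 8, the planned order in 4.6 and 13.3 | Before Cycle 8, the permitted exception |
| Scan after Cycle 8 (7.5, 15.3) | Nodule present | No disease |
| 9.2 Stage IV clause | Event | No event |
| 4.6 unresectability sentence | Not triggered | Not triggered |

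The text supports reading the planned resection as falling after the last cycles. In both sections it follows the instruction to give the final cycles, and the next sentence treats earlier surgery as the exception.

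**2. Who is affected.** Metastases that disappear need no operation. Transplant candidates are to be cleared of metastases before transplant. Patients operated on earlier are disease-free by the scan. That leaves non-transplant Stage IV patients whose metastases persist through the last cycle.

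**3. What is not affected.** The plan states no Stage IV EFS target, so there is no EFS figure to reproduce. The Stratum 4 decision rule uses response after two cycles. With X1 ~ Bin(22, p) and X2 ~ Bin(19, p):

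- P(stop at stage 1) = P(X1 ≤ 9)
- P(success) = Σ over x = 10 to 22 of P(X1 = x) · P(X2 ≥ 23 − x)

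| | Computed | Stated in 9.2 |
|---|---|---|
| p = 0.45, stop at stage 1 | 0.435 | 0.435 |
| p = 0.45, not sufficiently effective | 0.900 | 0.90 |
| p = 0.65, success | 0.907 | 0.90 |

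The design reproduces, and no input is an EFS event. Overall survival runs to death from any cause, so the failure clause cannot change it. Aim 1.3.7 is a proportion operated on, so it is also unchanged.

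**4. Size, as an illustration.** Understatement of EFS = f × s. Here f is the share of Stage IV patients with metastasectomy after the last cycle, and s is the share of those who would otherwise stay event-free. The inputs come from Section 2.5.

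- f: in INT-0098, 2 of 38 patients metastatic at diagnosis had metastasectomy after liver resection. 2/38 = 5.3%.
- s: 6 of the 9 INT-0098 metastasectomy patients were long-term survivors. 6/9 = 0.667.
- f × s = 0.0526 × 0.667 = 0.035, or about 3.5 points.

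Holding f at 2/38 and varying s over the other series in that section:

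- SIOPEL-2, 3 survivors of 8 operated: 0.0526 × 0.375 = 0.020, or 2.0 points.
- SIOPEL-1, 4 of 4: 0.0526 × 1 = 0.053, or 5.3 points.

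The INT-0098 timing is relative to liver resection, not to the last chemotherapy cycle. The true f could therefore be below 2/38, down to zero.

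**The case against.** The difference between the Stage III and Stage IV clauses has an ordinary explanation. Stage III failure is judged after Cycle 4, exactly when surgery is planned, so surgery had to be named. By Cycle 8 or 10 the Stage IV primary is meant to be out already. This is fair, and the asymmetry alone proves nothing. It still leaves late metastasectomy uncovered, and the protocol itself plans that operation.

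The 4.6 sentence may concern the liver tumor only, since it follows text on removing the primary. It also does not say that unresectability is the only failure event. Both points stand. A reader might infer that a patient with a resectable nodule is declared event-free by 4.6, but the sentence does not go that far. What remains is that 4.6 and 9.2 apply different tests without saying how they fit together, and that 9.2 conflicts with the treatment sequence whichever way 4.6 is read.

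The affected group is small, no decision rule uses Stage IV EFS, and accrual closed on July 20, 2018, so changing the event now is a late endpoint change. All of this is correct. It limits the weight of the point and is the reason to keep results under the present wording as well.

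**Conclusion.** The point holds in a limited form. As written, 9.2 scores as failures some Stage IV patients whose remaining disease is due for protocol-planned resection, and their status turns on whether the surgeon operates before or after the last cycle. The effect is confined to EFS on the non-transplant pathway with metastases persisting through the last cycle.

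The size cannot be fixed from the documents. About 3.5 points, possibly less, rests on two assumptions: late metastasectomy as frequent as 2/38, and long-term survivors (6/9) taken as event-free. Changing only the second assumption moves the figure between 2.0 and 5.3 points.

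Two stronger readings are not supported.

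- A reader might take all 9 of the 38 INT-0098 metastasectomies as late and reach 9/38 × 6/9 = 6/38, about 16 points. Seven of the nine came before (2) or together with (5) liver resection, so that source does not support the figure. Nor should a rate be multiplied by the 43 planned for Stratum 4, which also includes non-metastatic patients with low AFP whom the Stage IV clause does not cover.
- A reader might infer that the exploration of metastasectomy announced in Section 2.5 is defeated. That exploration concerns survival, which is defined separately and is untouched.

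**What to change.** Reconcile 9.2 with 4.6 and 13.3:

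- Reword the Stage IV clause to parallel the Stage III clause, so that failure means disease still present once planned chemotherapy and any protocol-planned surgery (if attempted) are both complete.
- State one assessment time relative to that surgery, for event scoring only. The documents give no interval to borrow, so the study team must set and justify it. If no resection is attempted, date the event at the end-of-therapy evaluation.
- Say in 4.6 whether the unresectability sentence refers to the primary tumor only and how it relates to the 9.2 event.
- Because accrual has closed, report a sensitivity analysis under 9.2 as it now stands.

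The treatment sequence does not change. The cost is one reworded sentence, a clarifying line in 4.6 and one added analysis. A few events are removed or dated later. No new data are needed, because Sections 14.1.1 and 14.1.2 already require slides, pathology reports and operative reports for pulmonary metastasectomy.

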#### 3.1.5 Timing

All patients must be enrolled on AHEP0731 before protocol treatment begins. The date protocol therapy is projected to start must be no later than 42 days (28 days preferred) from biopsy or definitive surgery, whichever occurs latest, except in the case AHEP0731 therapy is started in an emergent situation (see [Section 3.2.2.b](#) below). **Investigators are strongly encouraged to enroll patients immediately following histological diagnosis and begin protocol therapy within 28 days of the initial surgical procedure.**

**Patients with Stage I and II tumors (see [Appendix III](#)) require rapid central pathologic review and enrollment of these patients on AHEP0731 must not occur until the results of rapid central pathologic review are known. Stage I and II tumor specimens are to be submitted immediately following histological diagnosis. Pathology specimens MUST be submitted no later than 14 calendar days (7 days preferred) from definitive surgery and be accompanied by a Rapid Review Transmittal Form found on the AHEP0731 protocol page of the COG website. If Stage I and II diagnostic specimens are not submitted within 14 days of initial surgery, the patient will **not** be eligible for this study. **Enrollment of Stage I and II patients onto this study must not occur until the results of rapid central pathologic review are known and these results must be provided by the institutional investigator on the AHEP0731 Eligibility CRF.****

Retrospective central pathologic review is also required for all other biopsied/resected specimens (liver and/or lung). Specimens must be submitted within 4 weeks from all biopsies/resections other than Stage I and II diagnostic procedures. These specimens will be submitted using the generic COG Specimen Transmittal form. See [Section 14.1.1](#) for details.

**All clinical and laboratory studies to determine eligibility must be performed within 14 days prior to enrollment unless otherwise indicated in the eligibility section below.**

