#### 4.4 Treatment for Low-Risk Patients (Stratum 2 - Regimen T)

Patients classified as low-risk **must** have tumor specimens submitted for rapid central pathology review prior to enrollment onto this study (see [Section 14.0](#) for details). Patients must sign consent giving permission to submit tumor specimens prior to shipment and cannot be enrolled on study or start treatment until the results of rapid review are known. Low risk patients will have the tumor completely resected at diagnosis and then receive 2 cycles (each cycle is 21 days) of adjuvant C5V. Patients **must begin protocol therapy within 42 days of definitive surgery to allow for recovery from any surgical complications. However, it is strongly encouraged that patients begin protocol therapy within 28 days of the initial surgical procedure.** Begin each cycle of Regimen T only when the absolute neutrophil count is  $\geq 750/\mu\text{L}$  and the platelet count is  $\geq 75,000/\mu\text{L}$ . **Note: All patients < 10 kg will have dosing in mg/kg.**

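### The Section 9.2 42-day rule lets post-enrollment outcome decide who is analysed for EFS, and it cites a clock that Sections 3.1.5, 4.4 and 8.1(f) do not use.

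*Combined protocol and SAP*

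**What the plan says.** Section 9.2 starts EFS at enrollment. Its analytic events include progression and disease at new sites, and neither depends on chemotherapy having begun.

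The next paragraph sets the analysis population for strata that receive chemotherapy:

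- Early deaths stay in: "All patients who die within 42 days of enrollment will be considered in the analytic plans below".
- Other non-starters go out: "All patients who survive more than 42 days after enrollment and whose protocol therapy prescribes chemotherapy but who do not have such systemic therapy started" (the limit is day 43) are left out of everything that follows. There is no exception for a patient who has already progressed.
- The stated basis is that Section 3 "requires that planned start of systemic therapy for patients whose protocol prescribed therapy includes chemotherapy must be within 42 days of enrollment".

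The sections that set the start-of-therapy rule use a different origin:

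- Section 3.1.5: "The date protocol therapy is projected to start must be no later than 42 days (28 days preferred) from biopsy or definitive surgery", whichever is later, with an exception for emergent starts.
- Section 4.4 (Stratum 2): patients "must begin protocol therapy within 42 days of definitive surgery".
- Section 8.1(f), as a reason for removal from protocol therapy: "Failure to begin protocol therapy within 42 days of initial biopsy or definitive surgery whichever occurs last".

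Further on, Section 9.2 limits the Hypothesis 1.1 (Stratum 2) analysis to patients who actually received that stratum's chemotherapy. Section 8.1 requires continued follow-up after protocol therapy ends unless consent is withdrawn.

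**The concern.** Whether a patient counts depends on what happens after the EFS clock has started. Take three Stratum 2 patients who never start C5V. One dies on day 40 and is counted as an event. One relapses on day 30, is alive on day 43, and is removed although a defined event has occurred. One dies on day 50 and is also removed.

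Stratum 2 is where this matters most. Primary aim 1.2.1 is EFS after chemotherapy is cut from four cycles to two, and the rule flags the strategy at 7 or more events in 51 patients. With so few events, one or two exclusions can change the decision. The only planned comparison with and without certain cases concerns discrepant diagnosis or atypical histology, so nothing in the plan would reveal the effect of this exclusion.

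The citation is a separate fault. The analysis rule relies on a requirement that Section 3 does not contain in that form.

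**Working it through.** **Inputs.** From Section 9.2, Hypothesis 1.1: n = 51; flag at 7 or more events; stated P(reject) = 0.90 at EFS 78% and P(accept) = 0.81 at EFS 89%. The number of untreated progressors is not given; I assume 1 or 2 of 51.

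**The plan's own figures.** With X ~ Binomial(51, 1 − EFS):

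| Cut-off | P(reject), EFS 78% | P(accept), EFS 89% |
|---|---|---|
| 7 or more, as worded | 0.952 | 0.673 |
| 8 or more | 0.900 | 0.806 |
| Stated | 0.90 | 0.81 |

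The stated probabilities match a cut-off of 8, not 7. That is a separate defect, so both cut-offs are carried below.

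**Effect of excluding progressors.** If a share k/51 of enrolled patients progress untreated and are removed, a true EFS of 78% in all enrolled patients appears among those analysed as 0.78 / (1 − k/51):

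- k = 1: 0.78 × 51/50 = 0.7956, event probability 0.2044.
- k = 2: 0.78 × 51/49 = 0.8118, event probability 0.1882.

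Acceptance is P(X ≤ c − 1). It is computed with the excluded patients not replaced (n = 51 − k) and with accrual continued to 51 starters, which the allowance of up to 60 enrolled makes possible.

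| Excluded progressors | 7-event rule, n = 51 − k | 7-event rule, n = 51 | 8-event rule, n = 51 − k | 8-event rule, n = 51 |
|---|---|---|---|---|
| 0 | 0.048 | 0.048 | 0.100 | 0.100 |
| 1 | 0.091 | 0.081 | 0.171 | 0.154 |
| 2 | 0.160 | 0.131 | 0.273 | 0.232 |

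**Effect of excluding event-free non-starters.** Apparent EFS is (0.78 − k/51) / (1 − k/51), that is 0.7756 for k = 1 and 0.7710 for k = 2. Acceptance under the 7-event rule becomes 0.0480 or 0.0475 without replacement, and 0.0416 or 0.0355 with 51 starters. All lie slightly below 0.048.

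**One data example.** Six events in 51 starters gives 1 − 6/51 = 88.2%, and the strategy is accepted. Add one excluded progressor and it is 7 events in 52, or 86.5%, which reaches the 7-event flag.

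**Clock.** If enrollment falls e days after surgery, the Section 9.2 window closes 42 to 43 days later, at day e + 42 to e + 43 after surgery. The surgery-based window closes at day 42. Stage I and II patients cannot be enrolled until rapid central pathology review is known, so e > 0 in Stratum 2. With e assumed to be 7 to 28 days, the Section 9.2 window closes at day 49 to 71. A patient could be off protocol therapy under 8.1(f) and still be in the Section 9.2 analysis set.

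**The case against.** **Treated patients are a legitimate target.** Stratum 2 is single-arm, with no randomization to protect, and aim 1.2.1 concerns children given resection followed by two cycles of C5V. A relapse in a child who never received C5V reflects surgery alone. This stands as a reason to report a started-chemotherapy set. It does not justify the rule as written, which is not a treated set either: it keeps untreated early deaths and drops other untreated patients. It also conflicts with the separate Section 9.2 limit to patients who received the chemotherapy.

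**The bias need not run one way.** A reader might infer that the rule can only favour reduced chemotherapy. The text does not support that. Refusals and logistical delays are dropped too, and removing those who stay event-free lowers apparent EFS slightly. Keeping untreated early deaths also counts against the strategy. The net direction depends on an unreported mix.

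**Exposure is narrow.** Stratum 3 feasibility needs at least one dose, and Stratum 4 response needs at least one dose of each agent, so those primary endpoints are largely unaffected. Stratum 2 tumours are grossly resected at diagnosis, and Section 9.2 says most patients in prior studies started on time. This stands and limits the likely size.

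**The clock difference excludes fewer patients, not more.** That is so for Stratum 2, since the enrollment-based window closes later. The contradiction between sections remains.

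**Conclusion.** The point holds on the text. Section 9.2 makes inclusion in the EFS analysis depend on post-enrollment outcome, and it attributes to Section 3 a clock that Sections 3.1.5, 4.4 and 8.1(f) do not use. The consequence is confined mainly to the Stratum 2 EFS rule and the secondary EFS estimates.

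The size is conditional. It assumes 1 or 2 excluded progressors in 51 and independent binomial events at a true EFS of 78%. Under the 7-event rule as worded, acceptance of that inadequate strategy then rises from 0.048 to 0.08–0.09 or 0.13–0.16. With no such patients the effect is nil.

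Two stronger readings should be avoided. One is that dropping an event amounts to moving the cut-off by one, which would give 0.100 and 0.18. That leaves the denominator and event rate unchanged, and 0.100 is also the error already implied by the plan's stated 0.90. The other is that all deaths are kept: deaths after day 42 without chemotherapy are excluded.

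**What to change.** 1. In Section 9.2, analyse EFS and survival from enrollment in all eligible enrolled patients, counting progression or death before chemotherapy as an event. Apply the Stratum 2 event rule to this set.
2. Report the patients who started chemotherapy as a sensitivity analysis, stating how many were left out, why, and their outcomes.
3. Amend the Section 9.2 sentence that limits the Hypothesis 1.1 analysis to patients given the chemotherapy. If it stays, non-starters remain excluded by that route.
4. Reconcile the 42-day clock cited in Section 9.2 with Sections 3.1.5, 4.4 and 8.1(f). Which clock should govern the start of treatment is for the sponsor to decide.

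The cost is a few sentences. No new data are needed: Section 8.1 requires follow-up after protocol therapy ends unless consent is withdrawn, and Section 9.2 plans follow-up of all eligible patients. The one drawback is that the primary EFS estimate may include a few children who never received C5V; the sensitivity analysis covers that.
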